4.1.2 Exclusion Criteria

Subject meeting any of the following criteria will be excluded from the study:

1. Subject is receiving or has previously received any treatment for RA other than the medications listed in the inclusion criteria for the treatment of RA. This includes but not limited to:
 - a. Prior exposure to any biological agent other than TNF α inhibitor(s).
 - b. Any prior use of SYK or Janus kinase (JAK) inhibitors.
 - c. Alkylating agents used within 6 months prior to Day 1 dosing.
 - d. Prior treatment with intra-articular, intramuscular, intravenous, trigger point or tender point, intra-bursa, or intra-tendon sheath corticosteroids in the proceeding 8 weeks prior to Day 1 dosing.
 - e. Any surgical procedure, including bone or joint surgery or synovectomy (including joint fusion or replacement) within 12 weeks prior to Day 1 dosing.
2. Live or live-attenuated vaccine within 4 weeks prior to Day 1 dosing or expected need for live vaccination during study participation including at least 4 weeks after the last dose of study drug.
3. Subject has had treatment with any other investigational device or medical product within 4 weeks or 5 half-lives prior to Day 1 dosing, whichever is longer.
4. Subject who (based on the investigator's clinical assessment, makes the subject an unsuitable candidate for the study) has any active or recurrent or history of any of the following infections:

- a. Hepatitis B virus (HBV): Serologic evidence of current/previous HBV infection based on the results of testing for hepatitis B surface antigen (HBsAg) and anti-hepatitis B core (anti-HBc) antibody as follows within 6 weeks of Day 1:
 - Subjects positive for HBsAg and/or positive for anti-HBc antibody (regardless of anti-HBs antibody status) are excluded.
- b. Hepatitis C virus (HCV): Positive test for antibody confirmed on a subsequent blood sample by RNA-PCR assay within 6 weeks of Day 1.
 - Subjects who are positive for hepatitis C antibody and negative for hepatitis C RNA-PCR assay performed on a subsequent sample will be eligible to participate.
 - Subjects who are positive for hepatitis C antibody and have a positive result for hepatitis C RNA-PCR assay performed on the subsequent sample will not be eligible to participate.
- c. Human immunodeficiency virus (HIV) 1 or 2: Positive test at screening.
- d. Mycobacterium tuberculosis (TB):
 - For subjects with a history of TB, they may be enrolled if the following conditions met:
 - o documented evidence of appropriate treatment, which must have been completed at least 4 weeks or 5 half-lives, whichever is longer, prior to Day 1 of dosing,
 - o have no history of re-exposure since their treatment was completed,
 - o have no clinical features of active TB, and
 - o have a screening chest x-ray with no evidence of active TB.
 - For subjects with an indeterminate result for interferon-gamma release assay (IGRA) or latent TB (defined as a positive result of IGRA with a negative examination of chest x-ray) at screening, the following conditions must be met:
 - o If the result of the IGRA is indeterminate at screening, retest can be performed once during the screening period.

- If the repeated IGRA result is indeterminate again or positive, the subject will be excluded from the study.
- If the repeated IGRA result is negative, the subject can be enrolled in the study.
- Note: QuantiFERON Gold will be tested in central laboratories for all subjects and will determine subject's eligibility with regards to TB.
- If subjects present with a history of latent TB, they may be enrolled if all of the following conditions are met:
 - have documented evidence of appropriate treatment (TB prophylaxis must have been completed at least 4 weeks or 5 half-lives, whichever is longer, prior to Day 1 of dosing),
 - have no history of re-exposure since their treatment was completed,
 - have no clinical features of active TB, and
 - have a screening chest x-ray with no evidence of active TB.
- e. Interstitial pneumonia that is judged by the Investigator/subinvestigator to be inappropriate for the subject to participate in this study.
- f. Granulomatous infections or other severe or chronic infection (such as sepsis, abscess or opportunistic infections, or invasive fungal infection such as histoplasmosis). A subject who has a past diagnosis with sufficient documentation of complete resolution >6 months prior to Day 1 can be enrolled.
- g. Chronic or recurrent infection (including herpes zoster) within 6 weeks prior to Day 1.
- h. Acute infection requiring oral antibiotics within 2 weeks or parenteral injection of antibiotics within 4 weeks prior to Day 1.
- i. Other serious infection as assessed by the investigator within 6 months prior to Day 1 (such as sepsis, abscess or opportunistic infections, or invasive fungal infection such as histoplasmosis).

5. Subject who has any condition that could confound the evaluation of the data or the effect of the study drug, such as:

- a. Any other inflammatory or rheumatic diseases, including but not limited to psoriatic arthritis, ankylosing spondylitis, spondyloarthritis, systemic lupus erythematosus, Lyme disease, or uncontrolled fibromyalgia. Subjects with inactive or well-controlled fibromyalgia will be allowed to be enrolled in this study if the disease does not impact the study assessments, as per the investigator's judgement. Subjects with Sjogren's disease secondary to RA are eligible.
- b. Any conditions significantly affecting the nervous system (ie, neuropathic conditions or nervous system damage) if it may interfere with the investigator's assessment on DAS including joint counts.
- c. Severe physical incapacitation (unable to perform routine self-care, has RA ACR functional status class 4 [Arnett et al 1988], or who cannot benefit from medication).
- d. Any other serious acute or chronic medical or psychiatric condition that may increase the risk associated with study participation or study drug administration or that may interfere with the interpretation of study.

6. Subject who currently has one or more of the following medical conditions which in the opinion of the investigator would put the subject at risk by participating in the protocol:

- a. Uncontrolled diabetes mellitus, even after insulin treatment.
- b. Uncontrolled hypertension (as defined by systolic blood pressure ≥ 160 mm Hg or diastolic blood pressure ≥ 100 mm Hg on >1 occurrence or as judged by the investigator).
- c. Clinically significant finding meeting any protocol exclusion criteria on chest x-ray. Chest x-ray must be obtained during the screening period, unless a radiograph lung imaging (ultrasound not acceptable) was obtained within 12 weeks prior to the screening visit.
- d. Evidence of cardiac conditions as defined by the following:
 - New York Heart Association (NYHA) class III or IV heart failure, severe uncontrolled cardiac disease (unstable angina), or myocardial infarction within the 6 months prior to Day 1.

- Clinically relevant or significant ECG abnormalities, including ECG and QT interval correction for heart rate (QTc) using Fridericia's correction formula (QTcF). Subject with prolonged QT interval (using QTcF) defined as QTc >450 ms for male and >470 ms for female at retest will be excluded at screening.
- e. Any uncontrolled, clinically significant respiratory disease (in the opinion of the investigator), including but not limited to chronic obstructive pulmonary disease, asthma, bronchiectasis, or pleural effusion.

7. Subject who has a history of any of the following medical conditions:

- a. Any malignancy within the 5 years prior to Day 1, except completely excised and cured squamous cell carcinoma, carcinoma of the cervix in situ, cutaneous basal cell carcinoma, or cutaneous squamous cell carcinoma.
- b. Lymphoma or lymphoproliferative disease or bone marrow hyperplasia.
- c. Organ transplantation, including corneal graft/transplantation.
- d. Previous diagnosis or symptoms suggestive of demyelinating disorders, including multiple sclerosis and Guillain-Barré syndrome.

8. Subject who has planned to receive any of the following prohibited medications or treatment(s) from the time of informed consent through any additional time periods indicated below:

- a. Live or live-attenuated vaccination.
- b. Any surgical procedure, including bone or joint surgery or synovectomy (including joint fusion or replacement) within 6 months after Day 1.
- c. High potency opiates including (but not limited to): oxycodone, oxymorphone, fentanyl, levorphanol, buprenorphine, methadone, hydromorphone, morphine, and meperidine. Subject should discontinue at least 4 weeks prior to Day 1.

9. Subject who has clinically significant (per investigator's judgment) history of drug or alcohol abuse within the last 6 months.

10. Female subject who is currently pregnant, breastfeeding, or planning to become pregnant or breastfeed during the study or within 6 months after the last dose of study drug.

4.2 Withdrawal of Subjects From the Study Treatment and/or the Study

4.2.1 Reasons for Withdrawal/Discontinuation

Subjects may withdraw from the study at any time and for any reason without prejudice to their future medical care by the investigator or at the study site. Every effort should be made to keep subjects in the study. The reasons for subjects not completing the study will be recorded.

A subject may be withdrawn from the study for any of the following reasons:

1. Noncompliance with the protocol.
 - Protocol violations may result in data that are not deemed evaluable (by the investigator) for a protocol analysis and/or may require subject(s) to be discontinued.
2. Pregnancy.
 - If a female subject becomes pregnant, she must discontinue study drug immediately.
3. A serious or intolerable adverse event(s) (AE[s]) that in the Investigator's opinion requires withdrawal from the study.
 - Upon occurrence of a serious or intolerable AE that in the investigator's opinion requires withdrawal from the study, the investigator will confer with the sponsor.
 - If a subject is discontinued because of an AE, the event will be followed until it is resolved.
4. Laboratory safety assessments that reveal clinically significant hematological or biochemical changes from the baseline values.
5. Symptoms or an intercurrent condition not consistent with the protocol requirements or that justifies withdrawal (eg, development of contraindications of use of study drug).
6. Lost to follow-up.
 - Subjects that are considered lost to follow-up, reasonable attempts must be made to obtain information on the final status of the subject.

- At a minimum, 2 phone calls must be made and 1 certified letter must be sent for documentation.

7. Death of the subject.
8. Early termination of the study by the sponsor.
9. The subject withdraws consent.

4.2.2 Handling of Withdrawals

Subjects who discontinue study treatment or active participation in the study will no longer receive study drug. When a subject withdraws from the study, the reason(s) for withdrawal shall be recorded by the investigator on the relevant page of the eCRF. Whenever possible, all subjects who discontinue study drug or withdraw from the study prematurely will undergo all end-of-study assessments.

Subject who choose to discontinue study drug treatment but continue to participate in the study should complete end of treatment visit as soon possible, preferably within 2 weeks. Afterwards, subjects should follow the regular visit schedule and adhere to all study procedures except for dispensing study drug and blood sample collection for optional exploratory research and validation studies.

Subjects who fail to return for final assessments will be contacted by the site in an attempt to have them comply with the protocol. Following a minimum of 2 documented unsuccessful telephone calls, a registered letter will be sent to the subject in a final attempt to ensure protocol compliance.

It is vital to obtain follow-up data on any subject withdrawn because of an AE or serious AE (SAE). In every case, efforts must be made to undertake protocol-specified, safety, follow-up procedures.

4.2.3 Replacements

The subjects who are randomized but not dosed will be replaced; replacement will be accomplished by randomizing one more subject in a sequential order. Subjects who are randomized and received at least 1 dose of study drug will not be replaced.

5 Study Treatments

Three dose levels of SKI-O-703 will be evaluated in separate cohorts: 100 mg BID, 200 mg BID, and 400 mg BID. The SKI-O-703 capsules will contain 100 mg of drug substance. Placebo capsules are filled with microcrystalline cellulose and magnesium stearate to match in color and weight.

5.1 Method of Assigning Subjects to Treatment Groups

Subjects will be randomly assigned in a 1:1:1:1 ratio to receive SKI-O-703 100 mg BID, 200 mg BID, 400 mg BID, or matching placebo. An interactive voice or web response system (IxRS) will be used to administer the randomization schedule. The randomization schedule will be generated using SAS software version 9.3 or later (SAS Institute Inc., Cary, North Carolina) for IxRS, which will link sequential subject randomization numbers to treatment codes. The randomization schedule will be stratified by prior anti-TNF α biologic agents use (Yes or No), the number of previous csDMARDs treatments (0~2 or ≥ 3), specific geographic region (APAC, EMEA, and NA), and PK/PD sampling (Yes or No). It will also use an appropriate block size, which will not be revealed.

5.2 Treatments Administered

Subject specific doses will be prepared and checked by blinded pharmacy staff and administered by appropriately trained blinded clinic staff as delegated by the principal investigator (PI) at the study site. The study drugs will be similar in number and appearance for each cohort to maintain the study blind. The following dosing scheme will be performed:

Cohort	Treatment Arm	Treatment per Dosing Timepoint	
		Placebo Capsule	SKI-O-703 100 mg Capsule
1	Placebo	4	-
2	SKI-O-703 100 mg	3	1
3	SKI-O-703 200 mg	2	2
4	SKI-O-703 400 mg	-	4

SKI-O-703 100 mg BID, 200 mg BID, 400 mg BID, and placebo will be administered orally. The study medication will be taken no later than 30 minutes after food.

Day 1 Dosing:

On Day 1, subject will be administered his/her first dose of study medication no later than 30 minutes after food with approximately 8 ounces (240 mL) of water by the study site personnel. The study site personnel will check the subject's mouth to ensure the study drug and entire volume of water was swallowed.

The second dose will be administered approximately 12 hours (± 2 hours) after the first dose. The second dose and subsequent doses will be self-administered by the subject. The subjects will be instructed to take study medication no later than 30 minutes after food.

Study Visit Day Dosing:

On study visit days, subjects will take the first dose of study drug no later than 30 minutes after food in the office under the guidance of study site personnel after all specified study tests and procedures have been completed, and new bottles of medication have been issued. However, if the visit cannot be scheduled within the regular dosing schedule for the first daily dose of a new cycle, the subject will be instructed to take the first dose at the regular schedule on that visit day from the bottle of the preceding cycle.

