Systemic exposure (C_{max} and AUC_{0-tau}) to SKI-O-592, M2, and M4 at 400 mg BID is predicted to be higher using the second approach [PK Parameter (200 mg BID, Day 7) \times 2]. For SKI-O-592, C_{max} and AUC_{0-tau} are predicted to be 6160 ng/mL and 14600 h \cdot ng/mL, respectively, and for M2 C_{max} and AUC_{0-tau} are predicted to be 994 ng/mL and 10000 h \cdot ng/mL, respectively, which is well within exposure levels calculated at the NOAEL in rats, and comparable to levels previously observed at 800 mg in Study OSCO-P1201. However, due to the very low M4 metabolite ratios (R_{met}) observed in rats compared to healthy volunteers, predicted exposure to M4 (644 ng/mL and 1970 h \cdot ng/mL for C_{max} and AUC_{0-tau} , respectively) is higher than the NOAEL exposure. Therefore, the dosing regimens proposed for this study (100 mg BID, 200 mg BID, and 400 mg BID) have been carefully selected to ensure that exposure to M4 does not exceed levels observed previously in healthy volunteers (Study OSCO-P1201, 800 mg).

Note: Because increases in systemic exposure to M4 were less than proportional to the dose of SKI-O-703 in Studies OSCO-P1201 and OSCO-P1202, and a reduction in M4 levels was observed over time in Study OSCO-P1202, both means of estimating C_{max} and AUC_{0-tau} for M4 at 400 mg BID are considered to be cautious approaches, potentially overestimating exposure at 400 mg BID.

Following single oral administration of 400 mg SKI-O-703 (Study OSCO-P1203), overall systemic exposure to SKI-O-592, M2 and M4 (AUC_{0-t} and AUC_{0-inf}) was comparable between the fed and fasted state, with 90% CI for the ratio (Fed/Fasted) contained entirely within the BE limits (0.80, 1.25) for SKI-O-592 and M4. By contrast, when administered in the fed state there was an approximate 56%, 43% and 46% reduction in maximum exposure (C_{max}) for SKI-O-592, M2 and M4, respectively, with an associated 2.5 to 4 hour delay in median t_{max} across all analytes. Since the overall extent of absorption is unaffected by the intake of food, but peak exposure is reduced, dosing is recommended with food in this Phase 2 study to reduce the potential for AEs which may be associated with spikes (ie, high C_{max}) in SKI-O-592, M2 and M4.

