5.7 Treatment Compliance

All doses must be taken in accordance with the original dosing schedule outlined at subject's Day 1 visit with the first dose. All doses must be taken approximately 12 hours (± 2 hours) after the previous dose in a consistent BID dosing pattern.

All IMP consumed must be documented clearly on the subject's dosing diary for accountability purposes. Each subject's dosing diary should be closely monitored by the site personnel at each study visit to ensure compliance with the original dosing schedule, beginning with the first dose of study drug has been maintained.

Missed Dose(s)

If the subject does not take their study drug dose at their regularly scheduled dosing time, they should take the dose as soon as possible but at least 8 hours before the next scheduled dose. If the next scheduled dose is within an 8 hours window, the dose is considered missed, and the subject should resume dosing with the subsequent dose on the original schedule.

If the subject experiences any drug interruption(s) they should notify their study site physician during the next scheduled study visit. Missed doses should be reported as a protocol deviation (or violations depending on the number of doses missed) may result in data that are not deemed evaluable (by the investigator) for a protocol analysis and/or may require subject(s) to be discontinued.

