Abbreviations: ACR, American College of Rheumatology; CD63, cluster of differentiation 63; DAS, disease activity score; EDTA, ethylenediaminetetraacetic acid; EOS, end-of-study; EOT, end of treatment; FSH, follicle-stimulating hormone; HBsAg, hepatitis B surface antigen; HIV, human immunodeficiency virus; HAQ-DI, Health assessment questionnaire disability index; HBcAb, hepatitis B core antibody; HCV, hepatitis C virus; hsCRP, high sensitivity C-reactive protein; PD, pharmacodynamic; PK, pharmacokinetic; PPD, purified protein derivative; RA, rheumatoid arthritis; TB, tuberculosis; WOCBP, women of child bearing potential.

^a When procedures overlap at the same timepoints, the vital parameters assessment will be performed first followed by laboratory parameters and other procedures (Section 6.4.2).

^b Subject who choose to discontinue study treatment, but continue to participate in the study should complete EOT visit as soon possible, preferably within 2 weeks. Afterwards, subjects should follow the regular visit schedule and adhere to all study procedures except for dispensing study drug, and blood sample collection for optional exploratory research and validation studies.

^c Any of the procedures may be performed at an unscheduled visit at the discretion of the investigator.

^d All study procedures on Day 1 must be completed prior to randomization in order to save time for IMP dispensation and postdose PK/PD sampling.

^e A complete physical examination should be performed at the time points specified. Interim physical examinations can be performed at the discretion of the investigator, if deemed necessary to evaluate AEs or clinical laboratory abnormalities (Section 6.4.1).

^f Vital sign measurements include systolic and diastolic blood pressure, pulse rate, respiratory rate, and oral temperature (tympanic temperature for Korean subjects). The subject must be seated for 5 minutes before all measurements are taken (Section 6.4.2).

^g Patient questionnaires and scales should be performed prior to any procedures and assessments. The HAQ-DI should be scored for all 8 categories (Section 6.3.3).

^h TB testing will be performed for all subjects within 28 days of Day 1. Positive diagnostic TB test, which is defined as positive QuantiFERON Gold test will be tested in central laboratories for all subjects and will determine subject's eligibility with regards to TB.

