6.4.3 Electrocardiograms

Single 12-lead ECGs will be obtained, after the subject has been in the supine position for at least 5 minutes, prior to randomization at Visit 1 and at subsequent visit as indicated in the schedule of events (Table 6-1). Electrocardiogram assessments will include comments on the rhythm; presence of arrhythmia or conduction defects; morphology; or ST segment, T wave, and U wave abnormalities; whether the tracings are normal or abnormal and whether there is any evidence of myocardial infarction. In addition, the following parameters will be measured and reported: RR interval, PR interval, QRS width, QT interval, and corrected QT interval from Fridericia's formula (QTcF).

The Investigator will determine whether any of the 12-lead ECG results are normal or abnormal and whether any abnormal results are clinically significant or not clinically significant. Clinical significance is defined as any variation in results that has medical relevance and may result in an alteration in medical care (eg, active observation, diagnostic measures, or therapeutic measures).

If a clinically significant change from screening is noted, the clinically significant value and the reason for clinical significance will be documented on the AE page of the subject's eCRF. The Investigator will continue to monitor the subject with additional assessments until the values have reached either the reference range or the values at screening or until the Investigator determines that follow-up is no longer medically necessary.

If ECG tracings are printed on a thermal paper, a certified copy must be made, attached to the original, and filed in the subject's records to ensure results remain clear and legible over time.

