9.6. Electrocardiogram

Single 12-lead ECGs will be obtained, after the subject has been in the supine position for at least 5 minutes, prior to randomization at Day 1 and at subsequent visit as indicated in the schedule of events. ECG parameters include RR interval, PR interval, QRS width, QT interval, and corrected QT interval from Fridericia's formula (QTcF). In addition, the 12-lead ECG results will be interpreted by the investigator and recorded as: normal; abnormal not clinically significant; or abnormal clinically significant.

Summary statistics of observed values and changes from baseline in ECG parameters will be provided over time. Frequency summaries of shifts from baseline interpretation results to post-baseline interpretation results at each visit will be provided. The number and percentage of subjects who have the following QTcF interval prolongation will be tabulated by treatment group over time. The descriptive summary of QTcF interval for the subjects with each specific interval prolongation will also be presented.

- QTcF > 450 msec
- QTcF > 480 msec
- QTcF > 500 msec

A subject data listing of ECG measurements will be provided by subject identifier, date of collection and ECG parameters.

10. Pharmacokinetic Analysis

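### Scheduled on-treatment ECGs and vital signs fall by default before the visit-day dose and none is scheduled after a dose, so the SAP's by-visit summaries mainly describe trough exposure

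*Protocol*

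**What the plan says.** **Order on visit days.** Protocol Section 5.2 has the first daily dose taken "in the office under the guidance of study site personnel after all specified study tests and procedures have been completed". Its one exception applies "if the visit cannot be scheduled within the regular dosing schedule for the first daily dose of a new cycle": the subject then takes that dose at the usual time from the earlier supply, so the visit's assessments follow the dose by an uncontrolled interval.

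**Dosing interval.** Section 5.7: "All doses must be taken approximately 12 hours" after the previous one, with a 2-hour tolerance either way.

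**ECG.** Section 6.4.3 specifies one supine tracing per visit. On when it is taken, the section says only this: "prior to randomization at Visit 1 and at subsequent visit as indicated in the schedule of events". No time relative to dose is given. SAP Section 9.6 repeats the timing: "prior to randomization at Day 1 and at subsequent visit as indicated in the schedule of events".

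**Vital signs.** Footnote a to Table 6-1 says that when procedures coincide, "the vital parameters assessment will be performed first followed by laboratory parameters and other procedures". Again no time relative to dose is given.

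**PK/PD subset.** Footnote n to Table 6-1 and Section 6.5.1 call for serial samples to 12 hours after the morning dose on Days 1 and 84, and for predose samples only on Days 14, 28 and 56. Where a PK draw coincides with a safety assessment, the safety assessment goes first. No ECG or vital sign reading is attached to any post-dose draw.

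**Why exposure matters to this protocol.** Section 1.5 lists cardiovascular effects among the potential risks. Section 1.3 says that 400 mg BID is new in humans, and it recommends dosing with food to "reduce the potential for AEs which may be associated with spikes" in SKI-O-592, M2 and M4.

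**Analysis.** SAP Sections 9.4 and 9.6 summarise vital signs and ECG parameters over time by treatment group. SAP Section 4.2 fixes by-visit summaries to the nominal visit. Time since dose appears in none of these sections.

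**The concern.** ECGs and vital signs compared with placebo are part of the secondary safety endpoint. If nearly all scheduled readings are taken when parent drug and M4 are near their lowest, similar results across arms show only that no effect was seen at trough. Read without that qualifier, the tables could be taken as evidence of no effect across the dosing interval, at a regimen with no earlier human data.

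The Section 5.2 exception adds a second problem. Subjects who dosed before the visit contribute post-dose readings to the same visit row. Nothing in the planned tables separates the two kinds of reading or shows how many there are of each.

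**Working it through.** **Timing.** A reading taken just before the next dose falls 12 ± 2 h after the previous one, so at about 10 to 14 h. This applies by default at four on-treatment visits: Days 14, 28, 56 and 84. The Day 1 ECG precedes randomization, and the follow-up visits are off treatment. The scheduled post-dose ECG or blood pressure readings number zero.

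**Day 84.** Section 5.2 cannot be followed literally by the PK/PD subset on Day 84, because their serial samples come after the morning dose. Those passages need reconciling, but neither places an ECG or vital sign reading after the dose.

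**Size.** The documents state no trough concentration, so there is no stated figure to reproduce. Inputs from Protocol Section 1.3:

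| Analyte | Predicted Cmax at 400 mg BID (ng/mL) | Predicted AUC0-tau (h·ng/mL) | Cmax reduction with food |
|---|---|---|---|
| SKI-O-592 | 6160 | 14600 | 56% |
| M2 | 994 | 10000 | 43% |
| M4 | 644 | 1970 | 46% |

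Formulas: Cavg = AUC0-tau / 12; fed Cmax = Cmax × (1 − food reduction). If the predose level is the lowest of the interval (assumption), it cannot exceed Cavg, so trough/peak is at most Cavg/Cmax. The fed figures also assume that the predictions are not already fed values and that the single-dose food effect carries over to steady state.

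- SKI-O-592: Cavg = 14600/12 = 1217. Bound = 1217/6160 = 20%. Fed Cmax = 6160 × 0.44 = 2710; bound = 1217/2710 = 45%.
- M4: Cavg = 1970/12 = 164. Bound = 164/644 = 25%. Fed Cmax = 644 × 0.54 = 348; bound = 164/348 = 47%.
- M2: Cavg = 10000/12 = 833. Bound = 833/994 = 84%, so the profile is nearly flat. Fed Cmax = 994 × 0.57 = 567, which is below Cavg and therefore impossible.

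The M2 result shows that the food adjustment is only approximate, so the fed bounds for the other two analytes are rough as well.

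**Why no point estimate is given.** With a one-compartment shape, an elimination rate of 0.42/h (from the predicted Cmax and AUC under a bolus shape) and AUC held at 14600, trough/peak for SKI-O-592 is about 1% for a bolus, 16% at an absorption rate of 0.3/h, 29% at 0.2/h and 40% at 0.15/h. The answer depends almost entirely on an absorption rate that the documents do not give.

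**The case against.** The strongest case against runs as follows.

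- **No peak-driven effect is shown.** Section 1.3 links peaks to adverse events in general, and Section 1.5 does not tie cardiovascular effects to Cmax. In the multiple-dose study (Section 1.1) there was no ECG trend. The slight blood pressure rises were at Days 16 and 21, apparently after the 7 days of dosing given in Section 1.3, and were not significant against placebo. This stands. A reader might infer that the trial would hide a known peak effect; the documents do not support that.
- **Similar exposure has been reached before.** Section 1.3 says that predicted parent and M2 exposure is comparable to that at a single 800 mg dose, and that doses were chosen to keep M4 within levels already seen. This lessens the worry. It does not replace 12 weeks of twice-daily dosing in patients on background therapy.
- **The dose-modification triggers still work.** A reader might infer that the Table 3-1 QTcF and blood pressure rows are disabled. They are not: the absolute QTcF row applies whenever a reading is taken, the blood pressure row requires a sustained rise, and unscheduled procedures are allowed.
- **Precise trough percentages are not available.** A reader might take the lower modelled values, about 1–16%, as the likely trough for SKI-O-592. Slower absorption gives 29–40%, so they should not be relied on.
- **A re-timed subset reading is weak evidence.** The subset is small, the ECGs are single tracings, and the baseline is predose and not time-matched. This stands and limits the gain.
- **Dose times may be recoverable.** Section 5.7 requires the diary to document all study drug taken. That makes the fix cheaper, but SAP Sections 9.4 and 9.6 do not use the information.

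**Conclusion.** The point holds as a limit on what the scheduled cardiovascular data can show. By default these readings describe exposure 10 to 14 hours after a dose, and the SAP pools them with an unknown number of post-dose readings. At 400 mg BID that is at most about 20–45% of peak for SKI-O-592 and 25–47% for M4. The bound rests on the protocol's predicted exposures, on a predose level no higher than the interval average, and at the upper end on a food adjustment that fails for M2. For an M2-driven effect the point has little force.

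The point is not that an effect exists, nor that the trial's safety monitoring fails. It is that an effect confined to the hours around peak could not be detected from the scheduled readings. The improvement is worth making because it is cheap; no primary analysis depends on it.

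**What to change.** 1. **Protocol 5.2, 6.4.2, 6.4.3 and Table 6-1.** Reconcile Section 5.2 with footnote n for Day 84. In the PK/PD subset, take the already scheduled Week 12 ECG and vital signs at a post-dose PK draw near the expected fed peak. The 4-hour draw is one example, to be confirmed against the sponsor's fed Tmax data, since Section 1.3 gives only a 2.5 to 4 hour delay. The safety-before-PK-draw order can stay; the vital-signs-first rule needs a matching edit. Compare with the subset's placebo subjects and plot QTcF and blood pressure change against the matched SKI-O-592, M2 and M4 concentrations, labelled exploratory.
2. **All subjects.** Record the time of the last dose with every ECG and blood pressure reading, using the dosing diary. In SAP 9.4 and 9.6, tabulate QTcF and blood pressure change separately for predose and post-dose readings.
3. **Report.** State that the other scheduled readings reflect mainly trough exposure.

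**Cost.** No extra procedure: one existing reading is re-timed in subjects already on site, one time field is recorded, and the SAP gains a table split and a plot. The subset loses its predose Week 12 reading and must be shown separately. It is small (minimum 24 subjects, about 6 per arm) and has no time-matched baseline. The change does not alter the readings that feed the Table 3-1 triggers on Days 14, 28 and 56. Item 2 therefore reaches the most subjects.
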